Measure of Adherence with Exercise: Women will wear the ActiGraph GT3X-plus activity monitor (Actigraph LLC, Pensacola, FL) on the wrist for a 4 day period at each of the 3 prenatal and 3 postpartum assessments (42 days total). The GT3X-plus actigraph is currently being used to measure activity among pregnant women in NHANES and provides activity counts, steps, MET-min/week, time in sedentary behavior, patterns of active and sedentary behavior, % wear time, subject position, and periods when the device has been removed. Pregnancy cutpoints will be based on our prior studies.¹³⁷⁻¹³⁹ The GT3X plus can be worn during periods of sleep to measure the amount and quality of sleep. Previous studies have reported reasonable validity under laboratory conditions among pregnant women¹⁴⁰ as well as under free living conditions.^{141,6,7} Assessors, blinded to study arm, will also administer the Pregnancy Physical Activity Questionnaire (PPAQ) at each of the 3 prenatal and 3 postpartum assessments. The PPAQ was developed and validated by our research team in the Baystate Medical Center population (NIH-NICHD R03-39341, PI: [name]) and recommended for use in pregnancy and postpartum.¹³⁸ Activity-specific measures will be summed to arrive at total daily energy expenditure in MET-hrs/wk and categories of activity type and intensity.

Measure of Adherence with Diet (24-Hour Diet Recalls): Assessors, blinded to study arm, will conduct 3 24-hour diet recalls during each assessment period.

D.13. Measures of Acceptability/Feasibility

After study completion, the assessor will administer a Satisfaction Survey which will assess a variety of factors relevant to the acceptability and feasibility of the intervention. For example, women will be asked what attracted them to the study, what barriers/facilitators enabled them to continue to participate, their response to the intervention materials, their perspectives on the assessment materials as well as the number of measures. Women who drop out of the study will also be contacted for a similar discussion which will include asking women what we could have done to keep them more engaged and barriers to participation. At the end of the study, staff feedback will also be queried using structured satisfaction surveys.

D.14. Staff Training and Quality Control

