Specific Aim #1, 2, 3: Impact of a Lifestyle Intervention on GWG and postpartum weight loss; biomarkers of insulin resistance; postpartum biomarkers of CVD risk. The primary analysis will evaluate differences in the change from baseline in weight gain measures, glycemia and other biomarkers of insulin resistance and cardiovascular risk factors between the groups (an intent to treat analysis). Initial analyses will describe the correlation of factors and investigate simple transformations for normality. The primary analysis will be based on a mixed model with random subject effects, including a common mean at baseline for the intervention groups, a period effect, and an intervention by period interaction.¹⁷⁰ The intervention by period interaction is a measure of the intervention effect, and corresponds to the estimate of an intervention effect in an analysis of covariance. The mixed model analysis will enable inclusion of time varying covariates such as depression, breastfeeding behaviors, and sleep, which may vary between baseline and follow-up for subjects. Equivalence of the intervention groups will be assessed by comparing the distribution of the potential confounders between each group. We will investigate established risk factors for weight gain (e.g., parity) and glycemia as well as degree and treatment for abnormality on glucose tolerance testing during pregnancy (e.g., diet, oral hypoglycemic and/or insulin) as potential confounders or effect modifiers. Generally, we will consider a change in the parameter estimate for the exposure (at least 15%), relative to that observed when not controlling for the variable as reflective of confounding. Effect modification will be evaluated by inspection of stratum specific odds ratios as well as by evaluating the statistical significance of interaction terms via likelihood ratio tests. We will also model the relationship between measured levels of exercise, sedentary behavior, and diet with each outcome, while adjusting for possible confounders using mixed effect linear regression models. We will test hypotheses with 2-sided tests. Finally, we will compare adoption and maintenance of behavior change (i.e., exercise, diet) in the intervention group relative to the control group by adding a fixed treatment group effect.

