At the time of recruitment (~10 weeks gestation), a blood sample to evaluate serum biomarkers associated with insulin resistance and other cardiovascular risk factors will be collected (termed "blood draw"). A total 700 microliters (uL) of serum will be collected which is equivalent to 1.5 milliliters (mL) or less than a teaspoon of whole blood. Physical activity, diet, and other covariates will also be assessed at recruitment. Subsequent assessments will be conducted at ~24-28 weeks gestation, after 32 weeks gestation, 6-weeks postpartum, ~6.5-months, and ~13-months postpartum. A urine pregnancy test will also be performed at the postpartum assessments. Women who are identified as having a positive pregnancy test will be removed from the study at the time of their positive pregnancy test and referred to their obstetric care provider. Measurements of compliance with exercise and diet will include activity monitors (worn for a 4-day period within each of these assessment time points), tracking the number of intervention sessions attended, number of booster calls participated in, number of assessments (e.g., questionnaires, blood samples) completed, as well as an assessment of degree of participation in physical activity and healthy dietary behaviors. No participants will be excluded from the study based on noncompliance. Assessments to measure other important covariates will also be collected at these assessment time points. Subjects will be under no obligation to complete the assessments, activity monitoring, or blood collections. Pregnancy and postpartum medical and laboratory records will be reviewed for obstetric and medical history, clinical characteristics of the index pregnancy, and laboratory results. All data will be used specifically for research purposes.

Potential Risks:

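### D.16 names one fixed treatment-group effect for both adoption and maintenance of exercise and diet change, and gives no visit-specific contrast to tell them apart

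*Combined protocol and SAP*

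**What the plan says.** The D.16 paragraph on Aims 1 to 3 describes three analyses.

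- The primary mixed model, "including a common mean at baseline for the intervention groups, a period effect, and an intervention by period interaction", of which it says: "The intervention by period interaction is a measure of the intervention effect". The outcomes given for it are "differences in the change from baseline in weight gain measures, glycemia and other biomarkers of insulin resistance and cardiovascular risk factors". Exercise and diet are not on that list.
- A regression with behaviour as a predictor: "We will also model the relationship between measured levels of exercise, sedentary behavior, and diet with each outcome".
- Last, the comparison of adoption and maintenance of exercise and diet change "in the intervention group relative to the control group by adding a fixed treatment group effect". No model, visit, window or contrast is named.

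The data would support visit-specific answers. D.12.5 schedules the activity measures "at each of the 3 prenatal and 3 postpartum assessments". Section E.1 adds: "Physical activity, diet, and other covariates will also be assessed at recruitment". It then lists the rest: "Subsequent assessments will be conducted at ~24-28 weeks gestation, after 32 weeks gestation, 6-weeks postpartum, ~6.5-months, and ~13-months postpartum". That makes one assessment before randomization at about 12 weeks (D.5) and five after it. Maintenance is described only in D.7, as a stage of change in which a new behaviour is kept up.

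**The concern.** Adoption is a question about the first months of the intervention, and maintenance is a question about the last visits. A single group coefficient gives one number for both. If that number is an average over visits, a strong effect in pregnancy that has gone by 1 year can still give a significant result, and a reader could take it as evidence that the change lasted.

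Exercise and diet are the behaviours that the intervention targets, so this comparison shows whether they moved and whether they stayed moved. If the model and contrasts are not fixed in advance, the analyst can also choose among averages and single-visit differences after seeing the data.

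**Working it through.** **Inputs.** From D.17 and Table 3: two-sided alpha 5%, 80% power, activity minutes with N=300, SD of change 38.05 and detectable difference 12.3; 264 women expected at 1 year, taken as 132 per arm. Correlation between visits is not given, so I assume 0.3, 0.5 and 0.7. The on/off effect patterns below are also assumptions.

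**1. The plan's own figure.** (1.960 + 0.842) × 38.05 × √(4/300) = 12.31, or 12.35 with the t distribution, against 12.3 stated. Power at 12.3 is 79.9%. The figure reproduces without the 20% covariate reduction, which would give 11.0.

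**2. What the added term measures, by reading.**

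- Behaviour as outcome, no group-by-period term: a weighted average of the arm difference over visits.
- Added to the primary interaction model: the term frees the baseline difference. The effects at each later visit sit in the interactions.
- Added to the regressions that have behaviour as a predictor: the term is an arm difference in the outcome at a given behaviour, so it does not compare behaviour at all.

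In none of these does the added term itself separate adoption from maintenance.

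**3. Pooled effect over the five post-baseline visits, effect lost at 1 year.** True effect 12.3 at four visits and 0 at the fifth, so the average is 4 × 12.3 / 5 = 9.84. SD of a woman's average change = 38.05 × √((1+4ρ)/5), where ρ is the correlation between change scores. SE = SD × √(2/132).

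| ρ | SD | SE | 9.84/SE | P(significant) |
|---|---|---|---|---|
| 0.3 | 25.2 | 3.11 | 3.17 | 89% |
| 0.5 | 29.5 | 3.63 | 2.71 | 77% |
| 0.7 | 33.2 | 4.08 | 2.41 | 67% |

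If the effect is gone at both 6 months and 1 year (average 7.38), the range is 44-66%. If it exists in pregnancy only (average 4.92), it is 23-35%.

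**4. Main effect over all six visits, effect lost at 1 year, N=300.** Here r is the correlation between raw measurements, in units of the raw SD. Effect = (4/6) × 0.3246 × √(2(1−r)), where 0.3246 = 12.35/38.05. SE = (2/√300) × √((1+5r)/6).

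| r | Effect | SE | Ratio | P(significant) |
|---|---|---|---|---|
| 0.3 | 0.256 | 0.0745 | 3.44 | 93% |
| 0.5 | 0.216 | 0.0882 | 2.45 | 69% |
| 0.7 | 0.168 | 0.1000 | 1.68 | 39% |

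Only in this version does a fully maintained effect shrink, to 5/6 = 83% of its size, because baseline counts as an outcome visit with no true difference.

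**5. A contrast at 1 year.** With no true effect at 1 year, a two-sided 5% test favours the intervention in 2.5% of trials.

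**6. Simulation check.** Settings: 4,000 trials, six visits, 132 per arm, equal between- and within-woman variance, effect lost at 1 year only. The 1-year group-by-period term was significant for the intervention in 2.8%, the six-visit main effect in 64%, and a single post-baseline effect with a common baseline mean in 94%. The last exceeds the 77% in step 3 because that model uses the baseline value to sharpen the estimate.

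**7. Price of the 1-year contrast.** At N=264 the detectable difference is (1.960 + 0.842) × 38.05 × √(4/264) = 13.1 minutes, and power for 12.3 is 75%. This is for simple change scores. The common-baseline model is at least as precise if its variance assumptions hold.

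**The case against.** The strongest reply is that D.16 never says visits are averaged. It speaks of adding a term and does not say that the interaction is removed. If the term joins the primary model, the interactions still give the arm difference in change at every visit, including 1 year, so both questions stay answerable. That stands. It does not settle the matter, because the plan names the added term as the comparison and does not point to the interactions.

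Table 3 also frames activity and calories as change from baseline. On that basis baseline is not an outcome visit, and a reader who infers that the plan shrinks every real effect to 83% goes beyond the text. That stands too. The pooled post-baseline figures in step 3 do not depend on counting baseline.

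No rule says that a significant group coefficient establishes maintenance. The percentages are therefore rates of a significant coefficient, not rates of a declared false result.

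Finally, exercise and diet appear in D.12.5 as adherence measures and are not named as outcomes in the D1 aims, although Table 3 lists physical activity and calories under Aim 1. This limits the weight of the point: it does not touch the primary weight and biomarker comparison. A 1-year difference alone is also not proof of a sustained change, since late adoption would produce it as well. The fix allows for that.

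**Conclusion.** The point holds as a conditional one. The one term named for this comparison cannot separate adoption from maintenance on any of the three readings, and a suitable model already stands in the same paragraph for other outcomes.

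On the plainest reading, an effect that has vanished at 1 year would still give a significant coefficient in about 67-89% of trials (post-baseline visits pooled, 132 per arm) or 39-93% (all six visits, N=300), against about 2.5% in favour of the intervention for a 1-year contrast. These ranges rest on the assumed correlations, an effect equal to Table 3's detectable difference, and abrupt loss. They are illustrations, not predictions.

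A reader might infer that the plan does average all six visits, or that it will declare maintenance where there is none. The documents do not support either: the sentence leaves the model open, and no decision rule is written.

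**What to change.** Replace the last sentence of the D.16 paragraph on Aims 1 to 3 so that it does the following:

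- Analyses exercise and diet with the model already stated for weight and biomarkers (common baseline mean, period, arm by period), and reports the arm difference with its interval at each post-baseline visit.
- Defines adoption as the mean arm difference over the 24-28 week visit and the visit after 32 weeks.
- Defines maintenance as the arm difference at 1 year, interpreted together with adoption and with the 6-week and 6-month differences.

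The protocol must also reconcile its statements on when the intervention ends. D1 has the postpartum part run to 6 months, D.6 has the intervention continue through a year, and the D.9 heading gives about 7 months. Until these agree, it is unclear whether the 1-year visit falls after the intervention.

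The cost is a few sentences and no new data. The downside is precision: the 1-year contrast rests on 264 women and has about 75% power for 12.3 minutes. Table 3 shows only N=300 for behaviour, so the 1-year figure should be added there.

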
D.12.2. Child Anthropometric Measures

Child anthropometric measures will be obtained within 24 hrs of delivery, 6 wks, 6 mos, and 1 yr postpartum and include measured weight on a calibrated scale, length using a measuring board, and subscapular (SS) and triceps (TR) skinfold thicknesses. We will calculate fetal growth as birth-weight-for-gestational-age z-score and ponderal index (PI) as birth weight (g) x 100/birth length (cm)³. Ponderal index in neonates is closely correlated with estimates of total body fat and thus may indirectly reflect neonatal adiposity.¹⁶¹ We will evaluate change from 0 to 6 mos and from 0 to 12 mos in weight-for-length z score (WFL-z), weight-for-age z score (WFA-z), and length-for-age z score (LFA-z). We will calculate age- and sex-specific scores using U.S.

national reference data (National Center for Health Statistics, CDC Growth Charts). We will use the sum of skinfolds (SS+TR) to estimate overall adiposity, and the ratio of skinfolds (SS/TR) to estimate central adiposity. These anthropometric factors correlate strongly ($r=0.84$) with estimates using total body electrical conductivity.¹⁶² We will measure waist and head circumference. Every 6 mos the staff will be retrained in the anthropometric measurements.

D.12.3. Maternal Information, Delivery Information

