We will consider the following factors as covariates: Social Support for diet and exercise will be measured via the Social Support for Exercise (SSE). The SSE has three subscales (Family, Friends, Rewards/Punishments) and acceptable internal consistency (alphas .61-.91) and criterion validity.¹ Clinical Characteristics of the Current Pregnancy: will be abstracted from the medical record utilizing customized software developed in our previous studies. Variables include: degree of abnormality on glucose tolerance testing during pregnancy defined as: 1) normal results on the screening 50-g OGTT; 2) failed screening test with normal results on the diagnostic 100-g test; 3) impaired glucose tolerance (IGT) defined as failed screening test and exceeded <1 cutpoints on the 100-g test; and 4) GDM defined as failed 50-g test and exceeded 2 or more cutpoints on the 100-g test;¹⁶³ treatment for abnormal glucose tolerance during pregnancy (e.g., diet, oral hypoglycemic and/or insulin); other pregnancy complications (e.g., hypertensive disorders, preterm birth, infection, cesarean delivery, NICU admission, Apgar score). Medical History: will include: personal history of GDM, family history of diabetes, previous infant with anomalies, still birth, or macrosomia, infertility, and parity. Sociodemographic Factors: will include income, level of education, and health insurance; acculturation via the Psychological Acculturation Scale,¹⁶⁴ language preference, and generation in the U.S. Smoking and Substance Use: Alcohol consumption, smoking, and drug use will be collected via questions from the Pregnancy Assessment Monitoring System.¹⁶⁵ Sleep: Pregnancy and postpartum sleep will be collected via The Pittsburgh Sleep Quality Index (PSQI).¹⁶⁶ Depression: Pregnancy and postpartum depression will be assessed via the Edinburgh Postpartum Depression Scale¹⁶⁷ validated in Hispanics.¹⁶⁸ Breastfeeding: History of breastfeeding and frequency and duration of current breastfeeding (i.e., exclusive breast feeding, % of mixed breast and formula feeding, exclusive formula feeding), timing of introduction of solids, and other breastfeeding behaviors and beliefs will be assessed via the validated Infant Feeding Questionnaire.¹⁶⁹ Postpartum Urine

Pregnancy Test and Postpartum Diabetes Screening (using ADA diagnostic criteria¹⁶³) will occur at each postpartum assessment.

D.12.5. Measures of Adherence

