Specific Aim #4: Evaluate the impact of a Lifestyle Intervention on the outcomes of offspring. We will evaluate the impact of intervention arm on the offspring outcomes using the methods described for Aim #1-3. We will also examine GWG and prenatal glycemic factors as predictors of glycemia and weight gain in early infancy and childhood. Important covariates are listed in the covariate section. In models focused on offspring weight gain as the outcome, we will additionally adjust for fetal growth (i.e., BW/GA z score).

Specific Aim #5: Evaluate the cost-effectiveness of the Lifestyle Intervention. We will use procedures developed in our prior studies examining the cost-effectiveness of our interventions.¹⁷¹⁻¹⁷³ We will calculate the ratio of average dollars spent per average incremental improvement in outcome (i.e., GWG, postpartum weight retention, and biomarkers of insulin resistance and CVD risk). Incremental improvement will be defined as the mean change score from baseline for each group, adjusted for baseline values of the outcome measure and other participant characteristics.

Accounting for Missing Data: Although every effort is made to avoid missing data, we plan to use propensity score techniques¹⁷⁴⁻¹⁷⁶ to evaluate the potential sensitivity of results to missing at random assumptions. Multiple comparisons will be addressed by carefully considering the biologic rationale of observed associations.

D.17. Power

To achieve power to detect clinically significant differences requires 300 participants (150 in each intervention arm) at the time of delivery. Based on observed rates in our 2 trials (R01DK074876 and

ASPH/CDC S3948), we conservatively expect 10% of women to leave the New England area, deliver elsewhere, or withdraw during pregnancy, and therefore will recruit 333 women over the 24 mos recruitment period. For offspring outcomes, we calculate that 4% will be excluded for very early preterm birth (<34 wks), miscarriage, or stillbirth resulting in 288 children at delivery. Over the following 1 yr, we conservatively project that an additional 8% of women will be lost to follow-up due to withdrawal or movement out of the New England area. Women who become pregnant again will be censored. Therefore, we expect 264 women and children at 1 yr postpartum.

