We calculated the smallest mean difference in change from baseline in the Lifestyle Intervention vs. the Health & Wellness Control arm which we could detect at 80% power using standard deviations based on our prior studies and the literature^{47, 177-180} using 2-sided tests with a significance level of alpha=5% (NCSS PASS 2008 software). For multiple regression models, we assumed that covariates accounted for 20% of the variation. Tables 3 and 4 show we have excellent power to detect even ‘small to medium’ mean differences, as defined by Cohen,¹⁸¹ ranging from ~0.30 to 0.35 SDs for a range of representative outcome measures. For example, we have 80% power to detect as small as a 2.4% difference (Table 3) in percent change in HbA1c between treatment arms. A comparable trial among Hispanics observed a 7.1% difference in percent change in HbA1c between treatment arms¹⁸² demonstrating that detecting this difference is well within the capability of the lifestyle intervention. For the categorical outcome of Compliance with IOM GWG guidelines, given our observation that 51% of overweight/obese Hispanic women exceeded guidelines in the study population, we have 80% power to detect a 30% reduction in risk or larger for exceeding IOM guidelines.

Table 3. Power Calculations Corresponding to Aim #1-3.	Projected sample size for analysis	SD for Change from Baseline	Smallest detectable mean difference in change from baseline between arms
Aim #1: GWG & Postpartum Weight Loss			
GWG (kg)	300	7.00	2.3
Postpartum weight loss	264	6.00	2.1
Physical activity (MET-hrs/wk>mod intensity)	300	2.89	0.9
Physical activity (minutes>mod intensity)	300	38.05	12.3
Total Caloric Intake (kcal/day)	300	64.90	22.4
Aim #2: Biomarkers of Insulin Resistance			
Glucose (mg/dl)	300	13.27	4.3
Insulin (pmol/l)	300	14.20	4.6
HbA _{1c}	300	0.26	0.1
HbA _{1c} (percent change)	300	7.4%	2.4%
Adiponectin (μg/ml)	300	3.40	1.1
Leptin (ng/ml)	300	5.50	1.8
HOMA	300	1.00	0.3
Aim #3: Postpartum Biomarkers of CVD Risk			
Total cholesterol (mg/dL)	264	38.38	13.3
Triglycerides (mg/dL)	264	83.06	28.7
HDL-cholesterol (mg/dL)	264	7.59	2.6
LDL-cholesterol (mg/dL)	264	33.83	11.7
Systolic blood pressure (mm Hg)	264	12.23	4.2
Diastolic blood pressure (mm Hg)	264	7.64	2.6
CRP (mg/dl)	264	4.50	1.5

Table 4. Power Calculations Corresponding to Aim #4.	Projected sample size for analysis	SD	Smallest detectable mean difference between arms
Aim #4: Offspring Outcomes at Delivery			
Cord glucose (mg/dl)	288	14	4.6

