Cord insulin (μ U/ml)	288	4.7	1.6
Cord adiponectin (μ g/ml)	288	9.7	3.2
Cord leptin (ng/ml)	288	13.6	4.5
Birthweight-for-gestational age z-score [fetal growth]	288	0.93	0.3
Birthweight (g)	288	640	212
Ponderal Index (g/cm ³)	288	0.3	0.1
Birthweight-for-length z-score (WFL-z)	288	0.77	0.3
Head circumference (cm)	288	1.1	0.4
Aim #4: Offspring Outcomes at 1yr			
Adiponectin (μ g/ml)	264	5.8	2
Leptin (ng/ml)	264	1.8	0.6
Weight-for-age z score (WFA-z)	264	0.98	0.3
Length-for-age z score (LFA-z)	264	0.94	0.3
Sum of skinfolds (mm)	264	4.2	1.5
Ratio of skinfolds	264	0.16	0.1
Waist circumference (cm)	264	2	0.7

D.18. Environment

In brief, Baystate Medical Center, the recruitment site, is the major medical resource in Western Massachusetts and the third largest acute-care hospital in New England, with 725 beds currently in service and approximately 4,500 deliveries per year. The School of Public Health and Health Sciences at UMASS maintains a micro computer research room for faculty, staff and students. Fifteen PC compatible microcomputers, a file server, a scanner and two laser printers are connected to the Department's Local Area Network (LAN). The LAN enables secure hard disk space for research projects that is accessible by multiple users and backed-up daily. [name] (Department of Laboratory Medicine, Harvard University) lab at Children's Hospital, Boston, MA is a fully equipped laboratory with all of the requisite centrifuges, water baths, pipetters, etc. required to do the hormonal assays.

D.19. Timeline

This is a 5 year study. The timeline allows 12 months for study start up and protocol development, 24 months of recruitment, and follow-up of the last remaining participant (an additional 18 months from last enrollment). Data analysis will be ongoing and the last 6 months of the study will be dedicated to final analyses and manuscript writing.

D.20. Limitations and Alternatives

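### Infant sex is not among the covariates named for the offspring analyses, which gives up a little precision on raw outcomes at almost no saving

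*Combined protocol and SAP*

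**What the plan says.** D.16, Specific Aim #4, sets out the offspring analysis in a few sentences. On the method: "We will evaluate the impact of intervention arm on the offspring outcomes using the methods described for Aim #1-3". On covariates: "Important covariates are listed in the covariate section". One further term is added, for some models only: "In models focused on offspring weight gain as the outcome, we will additionally adjust for fetal growth (i.e., BW/GA z score").

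The covariate section, D.12.4, opens with "We will consider the following factors as covariates". It then lists social support, clinical characteristics of the pregnancy, medical history, sociodemographic factors, smoking and substance use, sleep, depression and breastfeeding. Infant sex is not on the list, and D.16 does not name it.

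Sex does appear in D.12.2, for the growth scores: "We will calculate age- and sex-specific scores using U.S". national reference data. Table 4 in D.17 gives 16 offspring outcomes, of which four are z-scores. Randomization (D.5) takes place at about 12 weeks' gestation and is stratified by maternal age and pre-pregnancy BMI.

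**The concern.** The plan recognises that infant size depends on sex, because it standardises its growth scores for sex. It makes no matching provision for outcomes analysed in grams, centimetres, millimetres or concentration units. In those models any boy-girl difference stays in the residual.

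Infant sex is an unusually safe covariate here. It is fixed at conception, before randomization, so the arm cannot change it. It must also be on file, because the sex-specific scores cannot be computed without it. By contrast, several factors that D.12.4 does list arise after randomization, such as treatment for abnormal glucose tolerance, cesarean delivery, Apgar score and breastfeeding. The list therefore includes factors that the intervention could influence and leaves out a prognostic one that it cannot.

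What is at stake is efficiency: slightly wider confidence intervals and slightly lower power than the same children could give.

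**Working it through.** **Which outcomes are affected.** Table 4 has 9 outcomes at delivery and 7 at one year. The z-scores are birthweight-for-gestational-age, birthweight-for-length, weight-for-age and length-for-age. The remaining 12 are raw:

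- At delivery (7): cord glucose, insulin, adiponectin and leptin; birthweight; ponderal index; head circumference.
- At one year (5): adiponectin; leptin; sum of skinfolds; ratio of skinfolds; waist circumference.

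D.12.2 does not say outright that the birthweight-for-gestational-age reference is sex-specific. If it is not, the count is 13 of 16.

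**Reproducing the plan's figure.** Inputs for birthweight are 288 children (Table 4), taken as 144 per arm under the equal allocation in D.5; SD 640 g (Table 4); two-sided 5% and 80% power (D.17).

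- SE of the arm difference = 640 × √(4/288) = 75.4 g.
- Smallest detectable difference, two-sample t-test with noncentral t = 212.0 g. Table 4 prints 212 g.
- The normal approximation gives (1.96 + 0.84) × 75.4 ≈ 211.3 g.

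All 16 rows of Table 4 match at their printed rounding with this unadjusted formula. D.17 also assumes that covariates explain 20% of the variation in regression models. Applying that to birthweight gives 212.0 × √0.80 = 189.6 g, which is not the printed value. Table 4 is therefore an unadjusted calculation, and no gain from sex is already counted in it.

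**Adding sex.** Let R² be the share of outcome variance that sex explains. The documents give no value, so the range below is an assumption. The one degree of freedom lost is negligible at this sample size.

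- SE and detectable difference are multiplied by √(1 − R²).
- Power at 212 g = Φ(212 / (75.4 × √(1 − R²)) − 1.96).
- Equivalent number of children = 288 / (1 − R²).

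| Assumed R² | Fall in SE | Detectable difference (g) | Power at 212 g | Equivalent children |
|---|---|---|---|---|
| 0 | 0 | 212.0 | 80.26% | 288 |
| 1% | 0.5% | 211.0 | 80.65% | 291 |
| 2% | 1.0% | 209.9 | 81.04% | 294 |
| 5% | 2.5% | 206.7 | 82.22% | 303 |

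Worked line for 5%: √0.95 = 0.9747; SE = 75.4 × 0.9747 = 73.5 g; 212/73.5 − 1.96 = 0.92; Φ(0.92) ≈ 0.822.

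The gain over this range is about 0.4 to 2.0 percentage points of power. The percentage fall in SE is the same for any outcome with the same R². Where sex explains almost nothing, as may be so for some biomarkers, the gain is almost nothing.

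**The case against.** The strongest reply is that nothing here is wrong. A randomized comparison without adjustment for sex is valid, and no two sections contradict each other. That stands, and it fixes the weight of the point.

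Three further arguments have partial force.

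- **The covariate sentence is ambiguous.** It follows the sentence on weight gain and glycemia as predictors, so it may be meant for those observational models. The arm comparison refers instead to the Aim 1-3 methods, whose primary model carries no fixed covariate list. On either reading, infant sex is not prespecified for the arm comparison.
- **The plan does not forbid sex.** D.12.4 lists factors to be considered, and D.16 would treat a variable as a confounder if it moves the estimate by at least 15%. But sex is not named as a candidate, and that rule looks for confounding after the data are seen. It does not select for precision, and could bring sex into some models and not others depending on the results.
- **Table 4 is a set of representative outcomes for power, not the analysis specification.** Raw birthweight, for example, has a z-score counterpart. This reduces the importance of some rows but does not remove the raw measures.

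A reader might also infer a second harm: that a chance excess of boys in one arm biases the result. The documents do not support that. Under equal allocation and an even sex ratio (assumed), the difference in the proportion of boys has SD √(0.25 × 4/288) = 5.9 points. With an assumed boy-girl gap of 0.2 SD (128 g), this adds an SD of 0.0589 × 128 = 7.5 g to the arm difference, a variance of 56.9 g². With R² = 0.25 × 0.2² = 1%, the table's 1% row removes 1% of 75.4², which is the same 56.9 g². Chance imbalance and lost precision are one quantity. The unadjusted SE already includes it, and neither bias nor type I error inflation follows.

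**Conclusion.** The point holds as a minor, nearly free improvement. Infant sex is absent from the named covariates, 12 of the 16 Table 4 outcomes are raw, and the variable is already required elsewhere in the plan. The unadjusted analysis remains valid and unbiased.

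The size rests wholly on an assumed R² of 1% to 5%: a 0.5% to 2.5% smaller SE, a birthweight detectable difference of about 211 to 207 g instead of 212 g, and about 0.4 to 2 more points of power. It will differ by outcome and may be near zero for some.

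A reader might infer a larger benefit by assuming a stronger sex effect. At R² = 10%, for instance, the birthweight figure would be 201.1 g and power 84.2%. The documents give no boy-girl difference for any outcome, so they do not support such a value, least of all across 12 unlike measures. A reader might also want exact age at measurement added on the same grounds. That does not follow: age at assessment is determined after randomization, so the argument that makes sex safe does not cover it.

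**What to change.** In D.16, Specific Aim #4, add one sentence: every offspring comparison between arms whose outcome is not already a sex-specific z-score is adjusted for infant sex as a fixed, prespecified covariate, whatever the change-in-estimate rule shows. Add infant sex to the list in D.12.4, and state in D.12.2 whether the birthweight-for-gestational-age reference is sex-specific, so that it is clear which models take the term.

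The cost is these short text changes and one degree of freedom per model. No new data are needed, and the sample size need not change.
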